Artificial Intelligence validation trial for polyp detection: Pilot study

Date: 30-10-2019

Study number: s59405

AI validation study for polyp detection

DO NOT USE A ZOOM CAP DURING THE COLONOSCOPY

Any brand of endoscope can be used since we aim to develop a general system, independent of the brand or type.

A GPU computer is connected to the Panasonic AG-MDR25P recorder. This recorder is directly connected via SDI to one of the SDI output ports of the processor. The computer will then in real-time analyse the video that is provided by the processor and show the polyp detections by overlaying a green bounding box on a separate screen.

The endoscopist will perform his colonoscopy as always and he will only see the unaltered video feed from the endoscope processor. In the same room, a second human observer (who is experienced with the appearance of endoscopic video and polyps) will observe the second AI-enhanced screen connected to the computer. The procedure will then go as follows:

1. Start recording with the Panasonic recorder from insertion of the endoscope.
2. Take a still image when starting pullback from the caecum (to mark this point for easier analysis later). The second observer notes down the time indicated on the screen.
3. After the caecum has been reached, the second observer will take note of the following events during the rest of the procedure (by marking it in the attached document):

i. **OBVIOUS FALSE POSITIVES**

The AI system gives a positive prediction but it is an obvious false positive (e.g. stool, biopsy forceps, coagulation tip, diverticulum, air bubble, ...). These are nuisances caused by the system, but would never cause the endoscopist to take action. These detections are **NOT communicated** to the endoscopist.

ii. **OTHER FALSE POSITIVES**

The AI system gives a positive prediction but the endoscopist does not indicate the presence of a polyp. In this case, a polyp could potentially be missed. If this location disappears from the field-of-view of the endoscopist (i.e. out of the image), the second observer should notify the endoscopist and ask him/her to go back and inspect the location in question. Three outcomes are possible here:

1. The location did not contain a polyp, so it was really a false positive.
2. The location did contain a polyp, so it was an additional detection polyp by the system.
3. The location could not be re-identified

iii. **FALSE NEGATIVES**

A polyp was found by the endoscopist, but the AI system never identified this location to contain a polyp.

iv. **TRUE POSITIVES**

The AI system and the endoscopist found the same polyp (irrespective of who

was first).

4. At the same time, the endoscopist performs the procedure as he would typically proceed until he gets interrupted by the second observer. He then tries to find the location as instructed by the second observer and proceeds after the location has been confirmed to contain a polyp or not.
5. Stop recording when the whole procedure is over.

Additional information needed:

Please provide each video with the following information:

- Number of polyps present in the video
- For each polyp (in the order of appearance or by time indication of when they appeared)
 - o Histological report conclusion
 - o Size
 - o Polypectomy type
 - o Location
 - o Morphology
- Brand and type of endoscope that were used

Statistical analysis plan:

Pilot trial to determine:

- a) Performance of novel Artificial intelligence tool
- b) Power and sample size calculation for ideal set-up of large multicentre validation trial

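### Does scoring events only after the caecum, while listing polyps from the whole video, put the pilot's results at risk?

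*Combined protocol and SAP*

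**What the plan says.** The combined protocol and SAP sets three scopes.

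- **Recording.** Step 1: "Start recording with the Panasonic recorder from insertion of the endoscope". Step 5: "Stop recording when the whole procedure is over". The video therefore covers both insertion and withdrawal.
- **Event scoring.** Step 3: "After the caecum has been reached, the second observer will take note of the following events during the rest of the procedure". False positives, false negatives, true positives and AI-prompted additional detections are all logged in this window. A false negative, for example, is defined as "A polyp was found by the endoscopist, but the AI system never identified this location to contain a polyp".
- **Polyp list.** Under the heading on additional information, each video comes with the "Number of polyps present in the video" and then an entry "For each polyp (in the order of appearance or by time indication of when they appeared"). Each entry gives histology, size, polypectomy type, location and morphology.

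Step 2 supplies a landmark between the two phases: "Take a still image when starting pullback from the caecum (to mark this point for easier analysis later"). The second observer also writes down the time at that point.

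The SAP has two aims: the performance of the tool, and "Power and sample size calculation for ideal set-up of large multicentre validation trial". It names no metric, no denominator and no rule for joining the list to the event log.

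**The concern.** The list and the log describe different stretches of the procedure, and the list need not carry times. Three things could follow.

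1. A polyp removed on insertion has a histology entry but no scored event.
2. A distal polyp noticed on insertion and scored on withdrawal may stand first on the list and last in the log, because the two passes meet the bowel in opposite directions. The totals still agree, so comparing counts would not reveal the mismatch.
3. The list has no field for polyps the endoscopist had already seen on insertion. Such polyps are unlikely to become AI-only finds, so including them could lower the AI's apparent added yield.

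At stake would be any breakdown of detections by histology or size, including for AI-only polyps, and an added-yield figure that might feed the sample size of the later trial.

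**Working it through.** The documents give no sample size, event rate or insertion frequency, so there is no figure of theirs to reproduce. The check has three parts.

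**1. Does the scope difference affect sensitivity?** Let TP, FN and A be the logged true positives, false negatives and confirmed additional detections. All three come from the step 3 window. Whether sensitivity is taken as TP/(TP+FN) or as (TP+A)/(TP+FN+A), every term comes from the log and none from the list. A polyp removed on insertion enters neither numerator nor denominator. The documents never name the video's polyp count as a denominator.

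**2. Can linkage misalign?** Assume entry i on the list is matched to event i in the log, with nothing else used. Let D be a distal polyp and P1, P2 proximal ones, with only D seen on insertion.

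| Case | List order | Log order | Correct links | Counts |
|---|---|---|---|---|
| D seen on insertion, scored on withdrawal | D, P1, P2 | P1, P2, D | 0 of 3 | 3 and 3 |
| D removed on insertion | D, P1, P2 | P1, P2 | 0 of 2 | 3 and 2 |

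If instead all polyps are seen on both passes, the orders are exact reverses. Position matching is then right for 0 of 2, 1 of 3 or 0 of 4 polyps. If none is seen on insertion, this cause does not disturb the order at all.

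The failure needs every one of these conditions:

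- at least one polyp seen or removed on insertion;
- a list given without times;
- a log without times, locations or identifiers;
- an analyst who ignores location, size, morphology and polypectomy type;
- no look at the recording.

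The documents do not establish the third, since the event form is an attachment outside the supplied text. They give no support for the fourth or fifth: the descriptive fields are requested for every polyp, and the pullback image is taken expressly to help later analysis. Location bears directly on the distal and proximal reversal. An ordered list can be replayed against the marked video to place each polyp before or after pullback, even without written times.

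**3. Added yield.** Assume 110 endoscopist polyps and 10 AI-only polyps, with a fraction g of the 110 seen on insertion. None of these values comes from the documents. The AI-only share without the insertion-seen polyps is 10/(110(1 − g) + 10).

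| g | Calculation | Share |
|---|---|---|
| 0 | 10/120 | 8.3% |
| 0.10 | 10/109 | 9.2% |
| 0.20 | 10/98 | 10.2% |
| 0.30 | 10/87 | 11.5% |

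At g = 0.10 the shift is under one percentage point; at g = 0.30 it is about three. These shares answer different questions. The first row is the AI's contribution on top of everything the endoscopist finds when working as usual, including what is noticed on the way in. The others restrict attention to polyps not already seen. Step 4 has the endoscopist follow normal practice, so the first is a legitimate quantity and not a biased version of the others.

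**The case for a change.** The strongest case for a change is that the list's wording does permit order alone, that matching counts can conceal a complete mislink, and that no step for resolving mismatches is written down. Histology is the only listed item that establishes what a detected lesion was, so attaching it to the wrong event would spoil any breakdown by type. A time for each polyp and one tick box would cost almost nothing.

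The reading of the text stands, and so does the observation that insertion-seen polyps are not marked on the list. The consequence does not. The list is requested as an annotation of the video, so a distal polyp seen first and listed first is listed correctly. Matching by position is an assumption brought to the documents.

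The obvious remedies also have faults. A time of first appearance would not match a withdrawal event for a polyp first seen on insertion. Opening the scored window at the pullback mark would leave out any polyp scored between reaching the caecum and starting pullback, which step 3 currently includes.

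**Conclusion.** No change to the plan is needed. The scope difference is real, but it is missing data-form detail that analysts can fill sensibly from the polyp descriptions and the marked recording. Sensitivity from the event log is unaffected. Total mislinkage appears only under position-only matching, which the documents do not prescribe. The added-yield shift, from under one to about three percentage points for insertion-seen fractions of 10% to 30%, rests on assumed counts and on a choice of estimand that the SAP does not make.

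This conclusion assumes that the recordings are kept and can be consulted, and that the descriptive fields are completed. If the event form proves to hold no times or locations, linking some polyps would take video review. That is extra work, not a wrong result. A common polyp number on both forms would be a convenience, but no stated analysis depends on it.

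### Does leaving the observer's dismissals under step 3.i unchecked bias the AI's recorded performance enough to need a change?

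*Combined protocol and SAP*

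**What the plan says.** The second observer watches the AI screen and marks events from the caecum onward; the endoscopist sees only the plain feed. The four classes in step 3 work as follows.

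- **3.i, obvious false positives.** "The AI system gives a positive prediction but it is an obvious false positive", with stool, instruments, diverticula and bubbles among the examples. The stated reason for not passing these on is that "These are nuisances caused by the system, but would never cause the endoscopist to take action".
- **3.ii, other false positives.** If the endoscopist has not called a polyp and the location leaves the view, "the second observer should notify the endoscopist and ask him/her to go back and inspect the location in question". Three outcomes are listed, the second being "The location did contain a polyp, so it was an additional detection polyp by the system". The third is that the location could not be found again.
- **3.iii, false negatives.** "A polyp was found by the endoscopist, but the AI system never identified this location to contain a polyp".
- **3.iv, true positives.** "The AI system and the endoscopist found the same polyp (irrespective of who" came first).

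Step 1 is "Start recording with the Panasonic recorder from insertion of the endoscope", and step 5 stops the recording at the end, so video of the whole procedure exists. The SAP has two aims: (a) "Performance of novel Artificial intelligence tool" and (b) the sample size of a later multicentre trial. It names no endpoint, effect size or number of patients. The marking form mentioned in step 3 is not in the text available here.

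**The concern.** The two kinds of unmatched detection are treated differently. Under 3.ii the protocol accepts that a polyp may have been overlooked, sends the endoscopist back and records what was found. Under 3.i one person's live judgement is final. The endoscopist cannot contest it because he does not see the boxes, the list of examples is open-ended, and the visible text describes no later check.

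Additional detections are counted only as outcome 2 of 3.ii. A polyp wrongly dismissed under 3.i and not found by the endoscopist would add one to the AI's false positives and take one from its additional yield. Additional yield is what the tool contributes beyond the endoscopist, so it is a natural part of SAP aim (a) and could supply the effect size for aim (b). If the loss were large, the pilot would undersell the tool and could lead to an oversized multicentre trial.

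**Working it through.** The documents give no rate, sample size or power on this point, so there is no figure to reproduce. The check has three parts: trace the rules, size the effect on assumed inputs, and ask whether a check on the recordings would help.

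**1. Tracing a true polyp that the AI boxes**

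| Observer | Endoscopist | Final class | Effect on results |
|---|---|---|---|
| Passes on | Finds it unaided | 3.iv | Correct |
| Passes on | Misses it, then re-inspects | 3.ii, outcome 1, 2 or 3 | Counted as additional if confirmed |
| Dismisses | Finds it unaided | 3.iv | Correct, once the 3.i mark is removed |
| Dismisses | Misses it | 3.i | One false positive too many, one additional detection too few |

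Only the last row is wrong. Class 3.iii cannot be affected, because it requires that the AI never flagged the location and that the endoscopist found the polyp.

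**2. Size, on assumed inputs**

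Let q be the share of AI-detected, endoscopist-missed polyps that the observer passes on. If every location passed on is found again (3.ii outcome 3 never occurs),

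recorded yield = q × yield without the filter, so the shortfall is 1 − q.

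If that yield set the effect size of a later trial that had no such filter, with effect proportional to yield and n proportional to 1/effect², the planned n would be multiplied by 1/q².

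| q (assumed) | Shortfall | 1/q² |
|---|---|---|
| 0.95 | 5% | 1/0.9025 = 1.11 |
| 0.90 | 10% | 1/0.81 = 1.23 |
| 0.80 | 20% | 1/0.64 = 1.56 |

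In counts, assume 95 true positives, 5 false negatives and 10 polyps seen only by the AI:

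- Additional yield per 100 endoscopist-found polyps falls from 10 to 9, 8 or 7 when 10%, 20% or 30% of the ten are dismissed.
- False positives are overcounted by 1, 2 or 3.
- Sensitivity computed from the recorded polyps moves from (95 + 10)/(95 + 10 + 5) = 105/110 = 0.9545 to, at worst, (95 + 7)/(95 + 7 + 5) = 102/107 = 0.9533.

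The sample-size factors apply only if the later trial drops the filter. If it keeps the same filter, the pilot yield is the relevant one and the factor is 1.

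**3. Would a check on the recordings help?**

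The natural remedy is for another endoscopist, unaware of the live call, to re-read a random sample of dismissed clips. With no suspicious clip among n, the upper one-sided 95% limit is 1 − 0.05^(1/n): 2.95% for n = 100, 1.49% for n = 200 and 0.99% for n = 300, treating clips as independent. These are shares of *dismissed detections*, not values of 1 − q.

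To convert, assume 1,000 dismissals and 10 recorded additional polyps. A clean sample of 300 still allows 0.0099 × 1,000 ≈ 9.9 lost polyps, so q could be as low as 10/(10 + 9.9) ≈ 0.50. That does not exclude even the worst value in the table above.

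**The case for a change.** The strongest case for acting is that the rule trace is sound and the pilot as written cannot show that the error is rare. The 3.ii pathway exists because unmatched boxes may hide missed polyps, and it seems inconsistent to exempt one subset on a single unverified opinion. The recordings already exist, so re-reading every dismissed clip, not just a sample, would cost only staff time and would leave the live procedure alone.

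The first part stands: the misclassification can occur, and its frequency will be unknown. The rest is weaker.

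- A re-read of all clips avoids the sampling problem, but it needs an extra reader and a way to locate the clips. Logging each dismissal time is a new live task unless the unseen form already asks for it. Re-running the AI gives boxes without the observer's labels, and the visible text does not require times for the 3.ii events that would have to be separated out.
- A clip read afterwards as a possible polyp has no histology. The result would be a wider range for the yield, not a corrected value.
- Some human has to decide which boxes deserve a second look before any box can add a polyp. The observer plays that part here, and an endoscopist watching the boxes directly would also dismiss some. The yield of the AI with no human filter describes a use that the documents do not propose.

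**Conclusion.** The concern reads the rules correctly, but it does not call for a change. The error is confined to polyps passed over by two people: an observer chosen for familiarity with polyps on endoscopic video, who is looking at the box, and the endoscopist. The named examples in 3.i are mostly things unlikely to be confused with a polyp, so the loss is probably small, although the documents cannot confirm this.

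The direction is conservative. Additional yield is understated, false positives are overstated, and any effect on a later sample size is upward. The shortfalls of 5% to 20% rest wholly on assumed q, and the factors of 1.11 to 1.56 need in addition a later trial without a human filter.

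Not interrupting the endoscopist for nuisance boxes is a fair trade-off in a pilot, and a re-read would buy little certainty. Two small matters remain: describing the yield as that of the AI with an observer filter, and removing a 3.i mark from any polyp that ends up under 3.iv. Both are reporting and bookkeeping steps that competent analysts would take anyway, and neither alters the recorded additional yield. The unseen marking form may bear on the point, but the conclusion does not depend on it.

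### Step 3.ii has no outcome for a polyp the endoscopist had already seen but not signalled, so additional detections can be overstated (minor)

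*Combined protocol and SAP*

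**What the plan says.** The endoscopist works from the unaltered video feed, and a second observer watches the AI screen and marks events. Step 3.ii (other false positives) covers the case where "The AI system gives a positive prediction but the endoscopist does not indicate the presence of a polyp". The prompt is delayed: "If this location disappears from the field-of-view of the endoscopist (i.e. out of the image), the second observer should notify the endoscopist". The request is for a second look at that place. Three outcomes follow: no polyp, polyp, or location not re-identified. For the second, the rule is "The location did contain a polyp, so it was an additional detection polyp by the system".

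Step 4 describes the endoscopist's side: "the endoscopist performs the procedure as he would typically proceed until he gets interrupted by the second observer". After the prompt, "He then tries to find the location as instructed by the second observer". What is settled at that point is limited: he "proceeds after the location has been confirmed to contain a polyp or not".

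Step 3.iv (true positives) covers a polyp found by both the AI and the endoscopist, in either order. Under 'Additional information needed', five items are listed per polyp: histology, size, polypectomy type, location and morphology. The statistical analysis plan gives the performance of the tool as its first aim and names no measure.

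**The concern.** Outcome 2 of step 3.ii is the only category that captures polyps gained through the AI. It is meant to count polyps that the endoscopist would have missed, but what the observer sees is the absence of an indication, a term left undefined. These differ when the endoscopist recognises a polyp, gives no sign and moves on, for example meaning to return to it. He has no instruction to announce what he sees, so this is compatible with working as usual.

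That polyp leaves the image, triggers a prompt, is confirmed and is scored as an AI gain. At stake is whether the additional-detection count can be read as polyps found only because of the AI. If the pilot reports that count as part of performance, it may flatter the system. Silent recognition leaves no trace on the video, so if it is not asked about at the time it cannot be recovered later.

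**Working it through.** The documents give no polyp counts, rates or sample size, so there is no plan figure to reproduce. The check has two parts.

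**1. Following one polyp through the rules.** Suppose the AI flags a location, and the endoscopist sees the polyp there but gives no sign.
- Step 3.ii entry: AI positive, no indication. Met.
- Notification: the location leaves the image. Met, so the observer prompts.
- Step 4: the endoscopist returns, and the only question settled is whether a polyp is present. It is.
- Step 3.ii outcomes: outcome 1 (no polyp) and outcome 3 (not re-identified) do not apply. Outcome 2 does, and it carries no condition that the polyp was previously unseen.

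The polyp is therefore scored as an additional detection. This follows from the stated outcomes themselves.

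**2. Direction and scale, with assumed counts.** Let A be the polyps scored under 3.ii outcome 2, E the polyps scored as found by the endoscopist (3.iii plus 3.iv), and k the number of the A that he had already seen. Moving those k to where they belong gives

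additional yield = (A − k) / (E + k).

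Assume A = 10 and E = 110:

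| k | calculation | additional yield |
|---|---|---|
| 0 | 10/110 | 9.1% |
| 1 | 9/111 | 8.1% |
| 3 | 7/113 | 6.2% |

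The numerator falls and the denominator rises with k, so the scored figure is never below the corrected one by this route. The table shows direction and how much each polyp matters; it does not estimate how many there will be.

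**Sensitivity.** Per-polyp AI sensitivity is (TP + A)/(TP + A + FN), with TP from 3.iv and FN from 3.iii. Moving k polyps from A to TP leaves TP + A unchanged. With 100 assumed polyps, 5 of them never flagged, it is 95/100 = 95.0% whatever the value of k.

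**The case against.** The best defence is that the plan uses a workable, observable convention. The endoscopist has the whole in-view period to react, and a polyp that leaves the image without any sign is treated as not detected. Nothing suggests that silent recognition is common, and self-report after a prompt is not obviously better than an observable rule. The statistical analysis plan does not name additional yield, so no declared analysis is shown to be biased. Much of this stands: it makes the problem narrow and the grade minor. It does not supply an outcome for the case in question.

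A second defence is that the scoring form attached to the protocol was not available for this review and may record prior recognition. That is possible, and if so most of the remedy is already in place. Even then, the outcomes as listed still assign the polyp to the AI.

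A reader might infer more than the documents support:
- *The count could also be understated, because a polyp found after a prompt could be scored under 3.iv.* Outcome 2 of 3.ii specifically governs a polyp confirmed after a prompt. The remark in 3.iv that order does not matter reads naturally as the order of detection between the AI and an endoscopist who cannot see its screen.
- *The plan does not record whether a prompt came first.* The three outcomes of 3.ii follow the notification, so the observer's event record already captures it. Only prior recognition is absent from the supplied text.

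**Conclusion.** The point holds as a minor one. As written, step 3.ii credits the AI with every polyp confirmed at call-back, including any that the endoscopist had recognised without signalling. The resulting error goes one way, towards overstating additional detections. Its frequency cannot be known from the documents and is probably low, given the delayed prompt.

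Under the assumed counts, one already-seen polyp among ten lowers additional yield by about one percentage point and three lower it by about three. The consequence rests on additional detections being reported as part of performance, which the plan neither states nor excludes. It would be wrong to conclude that AI sensitivity is biased, since the error only moves polyps between two categories that both count as AI-positive. Nor do the documents show an effect on the sample size of the later trial, because they do not say which pilot quantity will feed it.

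**What to change.** Leave the call-back trigger in step 3.ii as it is. Redefining an indication to include stopping to inspect would remove the call-back for lesions that were inspected and dismissed, which step 3.ii exists to catch.

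1. At each call-back, record whether the endoscopist reports having already recognised a polyp at that location. Ask once it is clear which location is meant and, where possible, before the result is confirmed.
2. Add a fourth outcome to step 3.ii: polyp confirmed, endoscopist reports having already seen it.
3. Report additional detections twice: with the fourth outcome counted as AI-only, which is the present rule, and with it counted as found by both.

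The cost is one question and one tick box per call-back and one extra line in the results. If the attached form already has such a field, only the fourth outcome and the second result line are needed. The drawback is that the answer is a self-report given after a prompt and may be biased against the AI. Both versions are reported for that reason, and the gap between them shows how much the result depends on it.

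### Is an AI flag whose location cannot be found again coded in conflicting ways by step 3.ii, step 4 and the per-video record?

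*Combined protocol and SAP*

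**What the plan says.** Procedure step 3 is where events are recorded: after the caecum is reached, the second observer marks each one on an attached form. Category ii covers an AI flag on which the endoscopist did not act. If the location leaves the field of view, the observer asks for it to be inspected again. The step then says "Three outcomes are possible here". The first is "The location did not contain a polyp, so it was really a false positive". The second is that a polyp was there, which counts as an additional detection. The third is "The location could not be re-identified". The first two carry a classification and the third carries none, although all three sit under a heading that calls the category false positives.

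Step 4 describes what the endoscopist does meanwhile: "He then tries to find the location as instructed by the second observer", after which he "proceeds after the location has been confirmed to contain a polyp or not".

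The section on additional information needed asks, for each video, for the "Number of polyps present in the video" and, for each polyp, items such as "Histological report conclusion", size and type of polypectomy.

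The statistical analysis plan has two aims: (a) the performance of the tool, and (b) "Power and sample size calculation for ideal set-up of large multicentre validation trial". It names no metric, denominator or effect size.

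**The concern.** Read side by side, the sections seem to disagree about how a communicated flag can end. Step 3.ii has three results and step 4 has two. The per-video record has no place for a location that was never found again, since such a location can supply no histology, size or polypectomy type. One could conclude that the same event is undetermined in one section, without an end in another, and silently no polyp in a third. The category heading pulls towards counting it as false, while the lack of a classification pulls towards leaving it open.

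If so, two quantities would depend on an unstated choice: the positive predictive value of communicated flags, and the number of polyps added by the system. Communicated flags are the only source of added detections in this design. They therefore bear on aim (a) and are a natural input to aim (b). AI sensitivity against polyps that the endoscopist found would not be affected.

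**Working it through.** **Which sections assign a code?**

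| Section | Unit | Assigns a code? | Treatment of a location not found again |
|---|---|---|---|
| Step 3.ii | AI flag | Yes, on the form | Its own listed result (ii.3) |
| Step 4 | Endoscopist's workflow | No | Not named, but the wording is of an attempt, which can fail |
| Additional information needed | Polyp | No, describes polyps | Not listed |
| Statistical analysis plan | None stated | No | No rule |

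Only one row codes flags, so there is no second code to conflict with it. The per-video list also omits obvious false positives (category i) and confirmed false positives (ii.1), because its unit is the polyp. Absence from that list is therefore not a code of no polyp.

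**What can the choice of analysis rule move?** The documents give no counts, no frequency of ii.3 and no sample size, so there is no figure of the plan's own to reproduce. All counts below are assumed. Write a = ii.1, b = ii.2, c = ii.3.

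- Predictive value of communicated flags: b/(a+b+c) if all ii.3 are false, b/(a+b) if they are excluded, (b+c)/(a+b+c) if all are true. The range has width c/(a+b+c).
- Added detections: from b to b+c, a factor of 1 + c/b, defined only when b > 0.

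Take a = 20, b = 10, c = 5 and 110 polyps found by the endoscopist:

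- All false: 10/35 = 28.6% (exact 95% CI 14.6% to 46.3%).
- Excluded: 10/30 = 33.3%.
- All true: 15/35 = 42.9% (26.3% to 60.6%).
- Added yield: 10/110 = 9.1% (Poisson 95% CI 4.4% to 16.7%) to 15/110 = 13.6% (7.6% to 22.5%), with the denominator held at 110.

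Varying c gives 10/32 = 31.3% to 12/32 = 37.5% for c = 2, and 10/40 = 25.0% to 20/40 = 50.0% for c = 10.

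For the predictive value of all positive detections, excluding obvious false positives, take 80 true positives, 5 added detections, 20 confirmed false positives, 5 false negatives and c = 5:

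- All false: 85/110 = 0.773.
- Excluded: 85/105 = 0.810.
- All true: 90/110 = 0.818.
- Sensitivity per polyp: 85/90 = 0.944 or 90/95 = 0.947.

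**Aim (b).** If the later sample size scaled as 1/effect squared (assumed; the plan names no design), c/b = 0.5 would change it by 1.5² = 2.25. Sampling error alone on 10 added detections gives (0.167/0.0436)² ≈ 14.7.

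**Can an analyst get at these figures from the plan as it stands?** Yes. Each formula needs only a, b and c, and step 3.ii has all three marked separately.

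**The case for a change.** The best case for a change has three parts.

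First, step 4 does leave out a result that step 3.ii lists, so read literally it gives the workflow no end point when the location is not found. That is true as a matter of wording. But the sentence assigns no code, and its own verb allows for failure. It is a slip that could be tidied at any edit, and no count depends on it.

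Second, the analysis plan does not say whether ii.3 is counted as false, excluded or reported separately, and the effect is not always small. At twice the assumed counts (70 flags, 10 of them unresolved), the all-true value of 42.9% lies above the all-false interval of 18.4% to 40.6%. With c = 10 against a = 20 and b = 10, the all-true 50.0% already lies above the all-false interval of 12.7% to 41.2%. This stands: if unresolved flags are common, their handling matters. But the frequency is unknown, and the data needed to show the range are collected anyway. The silence on ii.3 is one instance of a two-line plan that defines no metric at all, not a rule that gives a wrong answer.

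Third, the text sets no standard of certainty between confirming that a site holds no polyp and failing to find the site. The two results are nonetheless defined differently: one says what the location contained, the other that it was not found. Any finer standard may be on the attached form, which is not part of the text available here, so its absence cannot be asserted.

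**Conclusion.** The concern does not call for a change. The mismatch between steps 3.ii and 4 is real but clerical. The per-video list does not code flags, and the recording step keeps the unresolved flag as a separate result. What remains is missing analysis detail that a competent analyst fills in the ordinary way, by reporting the three counts and showing both extremes where a proportion is quoted.

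On the assumed counts with 5 unresolved flags out of 35, the choice moves the predictive value of communicated flags by 5/35 = 14.3 percentage points, within sampling error. It moves the predictive value of all detections in the second illustration from 0.773 to 0.818. These sizes rest wholly on assumed counts, on metrics the plan does not name and, for aim (b), on an assumed scaling. The all-true end also assumes that every unresolved flag was a distinct polyp not found later. A high frequency of unresolved flags would widen the range, but it would be visible in the pilot's own data and would not invalidate any rule or figure in the plan.
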